SOP	standard operating procedure
TDF	tenofovir disoproxil fumarate (Viread)
ULN	upper limit of normal
WBC	white blood cell count
WHO	World Health Organization

SCHEMA

CCTG 595 Vitamin D Sub-study

Effect of Vitamin D Supplementation on Bone Turnover Markers during Tenofovir-Emtricitibine Pre-Exposure Prophylaxis in Men Who have Sex with Men

DESIGN	
CCTG 595 is an open-label clinical trial of the effect of text messaging intervention vs. standard of care on adherence to Truvada (tenofovir-emtricitibine) as PrEP in MSM at increased risk of HIV infection.
 
This sub-study is a matched case-control study, in which cases prospectively take vitamin D3 4000 IU/day beginning at week 24 of PrEP.

DURATION	Subjects will be followed for 6 months (24 weeks)
SAMPLE SIZE	50 eligible subjects will receive vitamin D and will be compared to 50 matched control subjects from CCTG 595 who are not participating in this sub-study.
POPULATION	HIV-negative men aged ≥ 18 years initiating CCTG 595, who are not taking bisphosphonates and do not have a history of osteoporosis, fragility fracture, or kidney stones, or use of tenofovir prior to entry into CCTG 595
REGIMEN	Vitamin D3 4000 IU/day from week 24 through 48 of PrEP with Truvada
ENDPOINTS	Primary endpoint will be changes in bone turnover markers from week 24 through week 48 in the vitamin D intervention group as compared to age- and BMI-matched controls
ANALYSIS	A sample size of 44 subjects per group will provide 80% power to detect a 20% change in P1NP means from week 24 through week 48 between matched cases and controls using a paired t-test with a two-sided $\alpha = 0.05$. To account for attrition, a sample size of 100 is proposed, including 50 vitamin D treated cases and 50 matched controls from CCTG 595.

1.0 HYPOTHESIS AND STUDY OBJECTIVES

1.1 *Hypothesis*

Supplementation with vitamin D 4000 IU/day will significantly blunt the increases in BTMs that occur after initiation of PrEP with Truvada.

1.2 *Primary Objective*

To compare the change in P1NP levels from week 24 through week 48 among subjects (cases) who receive vitamin D 4000 IU/day to the change in levels seen in matched unsupplemented controls.

1.3 *Secondary Objectives*

1.3.1 To compare the change in CTX levels from week 24 through week 48 among subjects who receive vitamin D 4000 IU/day to the change in levels seen in matched unsupplemented controls.

1.3.2 To compare the change in PTH level from week 24 through week 48 among subjects who receive vitamin D 4000 IU/day to the change in levels seen in matched unsupplemented controls.

1.3.3 To compare vitamin D levels at week 48 among subjects who receive vitamin D 4000 IU/day and matched unsupplemented controls.

1.3.4 To demonstrate the change in P1NP, CTX, PTH, and vitamin D levels from baseline to week 24 in both cases and controls.

2.0 INTRODUCTION

2.1 *Background and Rationale*

Current HIV treatment guidelines recommend combination antiretroviral therapy with three active ARVs and 7 of the 9 currently recommended initial combination regimens for ART-naïve patients include tenofovir disoproxil fumarate (TDF) ¹. While treatment with TDF-containing antiretroviral treatment (ART) regimens have proven durable, tolerable, and effective, TDF has well described toxicities, including greater loss of bone mineral density (BMD) in the first 48 weeks after ART initiation and an increased risk for fragility fracture ²⁻⁴. The FDA recently approved TDF given with emtricitabine (FTC) as a single daily fixed dose combination (FDC) pill (Truvada (TDF/FTC)) for Pre-Exposure Prophylaxis (PrEP) to prevent HIV acquisition for persons with increased risk for HIV infection. In studies evaluating the efficacy of TDF/FTC for PrEP, daily use has been shown to significantly reduce BMD ^{5,6} albeit to a lesser extent than that seen during initial treatment for HIV. Although TDF-containing PrEP has not yet been associated with increased fracture risk, reduced BMD is nonetheless a concern for patients and providers of PrEP. Thus, strategies are needed to attenuate or prevent BMD loss, particularly when TDF-containing PrEP will be given for prolonged periods of time. The mechanism by which TDF induces BMD loss is unclear but appears to be mediated

through a reduction in PTH levels and PTH-controlled calcium and phosphate metabolism⁷. Additional data from ATN 063 suggest that TDF induces a state of functional vitamin D deficiency⁸

Recently, Overton and colleagues reported a dramatic reduction in the magnitude of BMD loss during initial therapy of HIV infection with vitamin D (4000 IU/day) and calcium supplementation⁹ when co-administered with efavirenz/TDF/FTC ART. The amount of BMD loss at the hip measured by DXA over 48 weeks with vitamin D-calcium was approximately half that seen with placebo (-1.5% vs. -3.2%, respectively, $p < 0.001$), and was reduced to levels that would be expected with ART that does not contain TDF. Notably, the median daily vitamin D intake was low for the cohort (120 IU/day) while calcium intake approached recommended daily intake (810mg). Thus, these data provide a strong rationale to study prophylactic administration of daily oral supplemental vitamin D in subjects receiving PrEP with Truvada.

In this study supplemental calcium will not be used because: a) in ACTG 5280, calcium intake among untreated HIV-infected subjects was generally adequate⁹. It can be anticipated that the largely healthy HIV-uninfected subjects in CCTG 595 will have levels of intake that are higher than the diseased population in ACTG 5280. This suggests supplemental calcium will not be required for 4000 IU/d vitamin D's beneficial effects,

particularly in the CCTG 595 subjects; b) there is concern that multiple additional pills a day may influence adherence with the primary intervention used in CCTG 595.

3.0 STUDY DESIGN

CCTG 595 is an open-label clinical trial of the effect of a text messaging intervention vs. standard of care on adherence to Truvada as PrEP in MSM at increased risk for HIV infection (ClinicalTrials.gov Identifier: NCT01761643). Eligible subjects for this matched case control substudy will receive vitamin D 4000 IU/day for 24 weeks, from week 24 through week 48. In CCTG 595, plasma from participants are being collected and stored at entry and every 12 weeks. These plasma samples will be used to measure P1NP, CTX, PTH, and vitamin D levels in both cases and controls at entry, week 24, and week 48.

4.0 SELECTION AND ENROLLMENT OF SUBJECTS

4.1 *Inclusion Criteria*

4.1.1 All subjects must meet CCTG 595 inclusion criteria.

4.2 *Exclusion Criteria*

4.2.1 All subjects must meet CCTG 595 exclusion criteria.

4.2.2 Current or prior use of bisphosphonate therapy.

4.2.3 Current use of vitamin D supplements greater than 400 IU/day.

4.2.4 Current use of androgenic hormones or growth hormones.

4.2.5 History of nephrolithiasis (kidney stones).

4.2.6 History of fragility fracture.

4.2.7 No use of tenofovir prior to entry into CCTG 595

4.3 *Study Enrollment Procedures*

Once a candidate for study entry has been identified, details will be carefully discussed with the subject. The subject will be asked to read and sign the approved protocol consent form. Participation in this substudy is not required for continued participation in CCTG 595.

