9.2 Analyses

All analyses are ITT, unless specified otherwise. Evaluable subjects will be individuals who agree to participate in the vitamin D substudy. The primary endpoint analysis will use a paired t-test to compare the changes in P1NP levels from week 24 to 48 weeks between cases and matched controls. Secondary endpoint analyses will include comparison of changes in 25-OH vitamin D levels, PTH, and CTX and will be analyzed analogously to the primary endpoint. If parametric assumptions fail, the corresponding non-parametric test will be applied, in this case, the Wilcoxon signed rank test. Sensitivity analyses will include linear regression models that adjust for possible confounding covariates, such as dietary intake.

Matching: Concurrent controls who are not enrolled in the vitamin D substudy who are reporting supplementation with ≤ 400 IU of vitamin D/day will be matched 1:1 by randomization arm in the CCTG 595 main study (text messaging arm vs. standard of care), age (± 5 years), race/ethnicity, season of study entry, and BMI (± 3 kg/m²).

REFERENCES

1. DHHS Panel on Antiretroviral Guidelines for Adults and Adolescents. Guidelines for the use of antiretroviral agents in HIV-1-infected adults and adolescents. 2014; <http://www.aidsinfo.nih.gov/ContentFiles/AdultandAdolescentGL.pdf>. Accessed May 1, 2014.

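### Vitamin D sub-study: section 4.2 and the Schema disagree on who is excluded, and the control-selection rule carries over only the vitamin D limit, so people barred as cases on bone-related grounds can serve as controls

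*Protocol*

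**What the plan says.** All references are to the vitamin D sub-study appended to the protocol unless stated otherwise.

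- **Section 4.2, Exclusion Criteria.** Item 4.2.7 reads "No use of tenofovir prior to entry into CCTG 595". Other items are "Current or prior use of bisphosphonate therapy" (4.2.2), vitamin D supplements above 400 IU/day (4.2.3), "Current use of androgenic hormones or growth hormones" (4.2.4), kidney stones (4.2.5) and "History of fragility fracture" (4.2.6). Item 4.2.1 asks that all subjects meet the main study's exclusion criteria.
- **Schema, Population row.** It describes men "who are not taking bisphosphonates and do not have a history of osteoporosis, fragility fracture, or kidney stones", and continues "or kidney stones, or use of tenofovir prior to entry into CCTG 595".
- **Section 9.2, Matching.** The rule begins "Concurrent controls who are not enrolled in the vitamin D substudy who are reporting supplementation with" and sets the limit at 400 IU/day or less. Matching is 1:1 on main-study arm, age, race/ethnicity, season of entry and BMI.
- **Section 9.2, Analyses.** The primary test is a paired t-test on the change in P1NP from week 24 to week 48. Covariate adjustment appears only as a sensitivity analysis, with dietary intake as its one named example.

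**The concern.** There are two separate problems.

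First, 4.2 is the numbered list a site would screen from, and it does not agree with the Schema. On tenofovir the two are opposite. On other items, one place excludes people whom the other admits.

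Second, vitamin D is not allocated at random. Comparability of cases and controls therefore rests on eligibility and matching. The endpoint is a marker of bone formation, and the sub-study judged several bone-related factors important enough to exclude from its cases. If controls are not held to the same exclusions, any effect of those factors on the P1NP change enters the contrast from one side only. None of them is a matching factor.

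**Working it through.** **Step 1: section 4.2 beside the Schema**

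| Item | Section 4.2 | Schema, Population |
|---|---|---|
| Prior tenofovir | 4.2.7: no prior use is the excluding condition | Population without prior use |
| Osteoporosis | Not listed; nearest item is fragility fracture (4.2.6) | Excluded |
| Bisphosphonates | Current or prior use (4.2.2) | Current use only |
| Androgens, growth hormone | Excluded (4.2.4) | Not mentioned |
| Vitamin D above 400 IU/day | Excluded (4.2.3) | Not mentioned |
| Fragility fracture, kidney stones | Excluded | Excluded |
| Main-study exclusions | 4.2.1, read literally, requires subjects to fall under them | Not mentioned |

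**Step 2: which exclusions reach the controls**

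Section 4.2 has six items specific to the sub-study (4.2.2 to 4.2.7), and the Schema adds osteoporosis: 6 + 1 = 7. Section 9.2 applies one of these to controls, the vitamin D limit. That leaves 7 − 1 = 6. Kidney stones read more as a safety item for vitamin D than as a bone-marker confounder. The remaining five are bisphosphonates, androgens or growth hormone, fragility fracture, osteoporosis and prior tenofovir.

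**Step 3: could section 4 be read as binding controls anyway?**

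Section 3.0 says that eligible subjects receive vitamin D. Section 6.0 names subjects and controls as separate groups. Section 9.2 defines evaluable subjects as those who agree to take part. Enrolment under 4.3 is by consent to the sub-study, which controls by definition have not joined. No stated step screens them. A person refused as a case for bisphosphonate use is simply not enrolled, and so falls within the control definition.

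**Step 4: does main-study entry already remove these people?**

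Not fully. Main protocol 4.2.5 bars current antiretroviral use, but 5.4.1.5 exempts FTC/TDF given as PEP or PrEP from the prohibited drugs. Entry therefore does not guarantee a tenofovir-naive control.

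**Step 5: possible size**

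The plan gives no figure to reproduce. If a fraction *f* of controls has a P1NP change shifted by *s* points, and no case is affected, the contrast moves by *f* × *s*. Both inputs are assumptions:

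- low end: 0.02 × 10 = 0.2 points;
- middle: 0.10 × 20 = 2 points;
- high end: 0.20 × 40 = 8 points.

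Against the 20-point effect in section 9.1 this is 0.2/20 = 1% to 8/20 = 40%. For scale, section 9.1 assumes an SD of the change of 40%, so the high end supposes that a fifth of controls are shifted by a full SD.

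**The case against.** The strongest reply has four parts.

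- **Item 4.2.7 is a drafting slip.** The Schema shows the other reading, and 4.2.1 slips in a similar way, so few sites would be misled. This is probably right. A reader might infer that the sub-study really enrols only tenofovir-experienced men; the documents do not support that. The list still needs correcting, because it is the screening list.
- **The osteoporosis gap is narrow.** Bisphosphonate use and fragility fracture already cover part of that group. This stands: what remains is osteoporosis without fracture and without bisphosphonate treatment.
- **Controls are not unscreened.** A reader might infer that none of the exclusions apply to them. That goes too far: the vitamin D limit applies, and controls have passed main-study eligibility. The Schema also calls them control subjects, and its Population row is not expressly confined to cases. At best this makes the text ambiguous, and step 3 shows that most of it points the other way.
- **The endpoint is a change, not a level.** A fixed history such as an old fracture or past tenofovir matters only if it alters the slope from week 24 to week 48, and both groups take study TDF/FTC from baseline. This stands and may shrink the bias for historical factors. It is weaker for ongoing factors such as current hormone or bisphosphonate use. The sensitivity regression has an open covariate list, but it names none of these factors and is not the primary analysis.

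**Conclusion.** The point holds in two parts. Section 4.2 and the Schema contradict each other on tenofovir and differ on osteoporosis, bisphosphonates and hormones; 4.2.1 needs rewording. The control rule omits five bone-related exclusions, so a non-randomised comparison differs by design on factors the sub-study chose to exclude.

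A reader might infer that the P1NP comparison is biased by a known amount or in a known direction. The documents support neither: they give no prevalence of these factors among controls and no effect of them on the 24-week change. The range of 0.2–8 points rests wholly on the assumed fractions and shifts, and the change endpoint may pull it down. Nothing here touches the main trial's primary analysis. The correction is still worth making, because it is cheap and the text as written permits the imbalance.

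**What to change.** 1. Reconcile section 4.2 with the Schema so that both give one list. Settle the direction of 4.2.7, the wording of 4.2.1, whether osteoporosis is excluded, whether bisphosphonate use is current only or current and prior, and whether the hormone exclusion stands.
2. State in section 9.2 that controls must meet the same reconciled bone-related exclusions as cases.
3. State how this is verified. Current use can be read from the main-study concomitant medication records (main protocol 6.3.4), and history items from the medical history where recorded (6.3.2, which does not name fracture or osteoporosis). Main-study records alone will not do for past drug use, because the medication history in 6.3.3 covers only the 30 days before entry. Past bisphosphonate or tenofovir use needs a brief question or chart check, or should be acknowledged as unverified in controls.

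The cost is some rewording, a small added check and a somewhat smaller control pool. The pool is at most 400 − 50 = 350, and fewer in practice, since controls must also have week 24 and week 48 samples, meet the vitamin D limit and match on five factors.

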5.0 STUDY TREATMENT

5.1 *Study Product Formulation and Preparation*

Vitamin D capsules will be supplied as 2000 IU capsules and will be taken as two capsules once daily. Store at 15°-30°C (59°-86°F). Do not expose to excessive heat or moisture.

5.2 Concomitant Medications

All concomitant medications will be recorded on existing CRFs for CCTG 595, with particular attention to vitamin D content of dietary supplements. Use of >400 IU of vitamin D3 in any dietary supplement (such as a multivitamin) will be prohibited.

6.0 CLINICAL AND LABORATORY EVALUATIONS

These will be performed as per the main study. All assays on subjects and controls will be performed on stored samples already being collected by the main study.

The only additional evaluation that will be performed will be calculating the average daily dietary intake of vitamin D and calcium from food. The participants will be asked to recall food items eaten over the last 3 days at the week 36 visit, and the calculator used in the ACTG 5280 study, which is adopted from the USDA database, will be used to quantify vitamin D and calcium intake.

7.0 CLINICAL MANAGEMENT

Instructions are provided only for toxicities related to study therapy (vitamin D). The grading system for drug toxicities is located in the Division of AIDS Table for Grading the Severity of Adult and Pediatric Adverse Events, Version 1.0, December 2004 (Clarification dated August 2009), located at the Division of AIDS Regulatory Support Center Web Site: <http://RSC.tech-res.com/safetyandpharmacovigilance>.

For toxicities attributed to vitamin D, investigators may discontinue therapy.

7.1 Toxicity

The general guidelines presented below apply to toxicities that are not specifically addressed in section 7.2.

Grade 1 or 2

Subjects who develop a Grade 1 or 2 AE or toxicity may continue vitamin D without alteration of the dosage. For subjects experiencing Grade 1 or 2 AEs who choose to discontinue vitamin D, the site investigator should contact the protocol chair, and encourage the subject to complete other aspects of CCTG 595.

NOTE: If subjects discontinue study therapies due to experiencing Grade 1 or 2 AEs, this should be noted in the CRF as the reason for discontinuation.

Grade 3

If the investigator has evidence that the AE was NOT caused by vitamin D, dosing may continue. Subjects who develop a Grade 3 AE or toxicity thought to be related to vitamin D, should have vitamin D withheld. The subject should be reevaluated weekly until the AE returns to Grade ≤ 2 or baseline, at which time the study therapies may be reintroduced, at the discretion of the site investigator or according to standard practice.

If the same Grade 3 AE recurs within 4 weeks of restarting treatment, vitamin D must be permanently discontinued. However, if the same Grade 3 AE recurs after 4 weeks, the management scheme outlined above may be repeated.

Subjects experiencing a Grade 3 AE requiring permanent discontinuation of vitamin D should be followed weekly until resolution of the AE and should be encouraged to complete the follow-up protocol study evaluations.

Grade 4

Subjects who develop a Grade 4 symptomatic AE or toxicity will have vitamin D permanently discontinued. Subjects experiencing a Grade 4 AE requiring permanent discontinuation of vitamin D should be followed weekly until resolution of the AE and encouraged to complete the follow-up protocol study evaluations.

7.2 Specific Management

7.2.1 Kidney Stones

Subjects who develop signs and symptoms consistent with urinary tract obstruction should have further evaluation. Subjects with evidence of a new kidney stone on study will be taken off vitamin D but continue to be followed on study.

8.0 CRITERIA FOR DISCONTINUATION

8.1 Permanent Treatment Discontinuation

- Drug-related toxicity
- Requirement for prohibited concomitant medications
- Subject develops a kidney stone (see section 7.3.1).
- Completion of treatment as defined in the protocol.
- Request by subject to discontinue treatment.
- Discontinuation of PrEP for any reason
- Clinical reasons believed serious by the physician, even if not addressed in the toxicity section of the protocol.

9.0 STATISTICAL CONSIDERATIONS

9.1 Sample size justification

In ACTG 5280, administration of vitamin D-calcium resulted in a significant reduction in

the magnitude of the rise in BTMs P1NP and CTX⁹. Because of more consistent association with changes in BMD with P1NP, this will be used as the primary surrogate marker to reflect bone health. Data on TDF effects on P1NP levels in the absence of HIV infection (e.g. during PrEP) are not available. In A5280, at week 24 P1NP increased by 60% with placebo and 36% with vitamin D-calcium ($p < 0.001$). If we anticipate that supplementation with vitamin D results in a decrease of similar magnitude from week 24 to week 48, then the expected intervention effect size is in the range of 24%. The SD of the change in P1NP at month 6 for the vitamin D-calcium group was 63%, but it is anticipated that the variability of P1NP levels in this study will be much less than that in HIV infected subjects undergoing a variety of pro- and anti-inflammatory changes after initiation of ART as in A5280. If we anticipate that in the absence of vitamin D supplementation that P1NP will increase by 20% and those receiving vitamin D will experience a reduction of this amount at week 48, then with an SD of the change in P1NP of 40%, a sample size of 44 cases and 44 controls will provide 80% power to detect a significant difference in the change in P1NP from week 24 to week 48 between cases and controls using a paired t-test with a two-sided $\alpha = 0.05$. In order to account for attrition, a sample size of 100 is proposed, consisting of 50 vitamin D treated cases and 50 matched controls.

9.2 Analyses

All analyses are ITT, unless specified otherwise. Evaluable subjects will be individuals who agree to participate in the vitamin D substudy. The primary endpoint analysis will use a paired t-test to compare the changes in P1NP levels from week 24 to 48 weeks between cases and matched controls. Secondary endpoint analyses will include comparison of changes in 25-OH vitamin D levels, PTH, and CTX and will be analyzed analogously to the primary endpoint. If parametric assumptions fail, the corresponding non-parametric test will be applied, in this case, the Wilcoxon signed rank test. Sensitivity analyses will include linear regression models that adjust for possible confounding covariates, such as dietary intake.

Matching: Concurrent controls who are not enrolled in the vitamin D substudy who are reporting supplementation with ≤ 400 IU of vitamin D/day will be matched 1:1 by randomization arm in the CCTG 595 main study (text messaging arm vs. standard of care), age (± 5 years), race/ethnicity, season of study entry, and BMI (± 3 kg/m²).

REFERENCES

1. DHHS Panel on Antiretroviral Guidelines for Adults and Adolescents. Guidelines for the use of antiretroviral agents in HIV-1-infected adults and adolescents. 2014; <http://www.aidsinfo.nih.gov/ContentFiles/AdultandAdolescentGL.pdf>. Accessed May 1, 2014.

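### The vitamin D sub-study's primary test leaves out week-24 P1NP, which will be measured in both groups and could be adjusted for at almost no cost

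*Protocol*

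**What the plan says.** All references are to the vitamin D sub-study appended to the protocol, unless stated otherwise. The SAP does not cover the sub-study.

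- **Primary analysis (9.2):** "The primary endpoint analysis will use a paired t-test to compare the changes in P1NP levels from week 24 to 48 weeks", comparing cases with their matched controls. No covariate enters. The Wilcoxon signed rank test is the fallback.
- **Groups (4.3, 9.2):** vitamin D is not randomised. Cases are main-study participants who choose to join, and controls are concurrent participants who did not join and who report no more than 400 IU of vitamin D a day.
- **Matching (9.2):** 1:1 on main-study arm, age, race/ethnicity, season of entry and BMI. P1NP is not a matching factor.
- **Adjustment (9.2):** "Sensitivity analyses will include linear regression models that adjust for possible confounding covariates, such as dietary intake". Week-24 P1NP is not named.
- **Data (3.0):** P1NP is to be measured in cases and controls at entry, week 24 and week 48.
- **Sample size (9.1 and Schema):** "a sample size of 44 cases and 44 controls will provide 80% power", "with an SD of the change in P1NP of 40" percent. The Schema gives "80% power to detect a 20% change in P1NP means from week 24 through week 48". Section 9.1 also says "the expected intervention effect size is in the range of 24" percent.

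**The concern.** Week-24 P1NP is the pre-intervention value of the outcome, so it would normally be the strongest available predictor of the week-48 value. A plan that measures it in everyone and does not use it beyond subtraction raises two questions.

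The first is precision. Subtraction fixes the weight on the week-24 value at 1. If the week-24 to week-48 correlation is below 1 and the variances are equal, that weight is too large and adds noise to a study of 44 to 50 pairs.

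The second is sensitivity to imbalance. Because the groups are self-selected, week-24 P1NP could differ between them. If the higher group then drifts back towards a mean shared with the other, part of the difference in change is drift. It would look like a vitamin D effect if cases start higher, and would hide one if they start lower.

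The planned regressions could address both points, but only as sensitivity analyses, and the one covariate they name is diet.

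**Working it through.** **1. The plan's own figure.** Inputs from 9.1 and the Schema are a 20-point effect (24 is also mentioned), SD of change 40, two-sided alpha 0.05, 80% power and a paired t-test.

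- Paired t-test, 20 points, 40 read as the SD of the pair difference: 34 pairs are needed, and 44 pairs give 90% power.
- Two independent groups, normal approximation, 24 points, SD 40: n = 2 × (1.96 + 0.84)² × 40² / 24² ≈ 43.6, so 44 per group. This matches, with a different effect and test. At 20 points the same form needs 63.
- Paired t-test, 20 points, 40 read as the per-person SD: 44 pairs result if the SD of the pair difference is about 46. That implies a within-pair correlation of changes of 1 − 46²/(2 × 40²) ≈ 0.34, which is not stated.

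The 44 can therefore be reached, but its basis is not stated. I use the two-sample form at 24 points as the reference because it returns 44, and show 20 points beside it.

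**2. Precision.** Let P1NP have the same variance σ² at both weeks, with correlation r. The documents do not give r, so 0.3 to 0.9 is assumed.

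- Variance of the change: 2σ²(1−r).
- Residual variance of week 48 given week 24: σ²(1−r²).
- Ratio: (1−r²) / [2(1−r)] = (1+r)/2.
- Residual SD: 40 × √[(1+r)/2].

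| r | Variance ratio | Residual SD | n per group, 24 points | Power at 44, 24 points | Power at 44, 20 points |
|---|---|---|---|---|---|
| no adjustment | 1.00 | 40.0 | 44 | 80% | 65% |
| 0.3 | 0.65 | 32.2 | 29 | 94% | 83% |
| 0.5 | 0.75 | 34.6 | 33 | 90% | 77% |
| 0.7 | 0.85 | 36.9 | 38 | 86% | 72% |
| 0.9 | 0.95 | 39.0 | 42 | 82% | 67% |

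These figures are for independent groups. For matched pairs the same algebra applies to the within-pair differences, with r replaced by the correlation of those differences between the two weeks. That correlation is also unknown.

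**3. Effect of an imbalance.** Let Δ be the case-minus-control difference in mean week-24 P1NP, and τ the true effect.

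- If both groups regress to a common mean, the expected week-48 difference is τ + rΔ. The change score then estimates τ + rΔ − Δ = τ − (1−r)Δ, and the adjusted model estimates τ.
- If Δ is a stable difference in level, the expected week-48 difference is τ + Δ. The change score then estimates τ, and the adjusted model estimates τ + (1−r)Δ.

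The error has the same size in both cases and falls on opposite methods. For the first case, σ = 40/√[2(1−r)] and the standard error of the unadjusted contrast is 40 × √(2/44) ≈ 8.53.

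| r | σ | Shift, Δ = 0.1σ | Shift, Δ = 0.25σ | Shift, Δ = 0.5σ | Rejection with no effect, 0.25σ | Rejection with no effect, 0.5σ |
|---|---|---|---|---|---|---|
| 0.3 | 33.8 | 2.4 | 5.9 | 11.8 | 10.7% | 28% |
| 0.5 | 40.0 | 2.0 | 5.0 | 10.0 | 9.0% | 22% |
| 0.7 | 51.6 | 1.5 | 3.9 | 7.7 | 7.4% | 15% |
| 0.9 | 89.4 | 0.9 | 2.2 | 4.5 | 5.8% | 8.2% |

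Every Δ here is hypothetical. With Δ = 0 the shift is zero.

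**4. Scale.** Section 9.1 states effect and SD in percent, while 9.2 speaks of changes in levels. The points above treat percentages as differences on one common scale, roughly 100 × log P1NP. If each person's percent change is analysed instead, the week-24 value is also the denominator and the conversion is only approximate.

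**The case against.** The case for leaving the plan alone is substantial.

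- A paired t-test on change is a recognised analysis of a 1:1 matched design, and it is the test that the sample size names.
- A change score removes any stable level difference between self-selected groups. In that setting the adjusted model is the one that is off, as step 3 of the working shows.
- No P1NP value decides eligibility or matching, so the usual route to regression to the mean, selection on an extreme value, is absent. An imbalance due to chance alone averages to zero: it is noise already carried in the standard error.
- There are safeguards: five matching factors, concurrent controls and a vitamin D limit. The planned regressions give diet only as an example. Objective 1.3.4 describes the change from baseline to week 24 in both groups, which allows a check of trends before vitamin D starts.
- The benefit depends on an unknown r, and at r = 0.9 the variance saving is only 5%.
- The sub-study is optional, is described as a pilot, and does not touch the main trial's primary endpoint.

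Most of this stands. A reader might infer that the paired t-test is biased by baseline differences, or that baseline adjustment would make the groups comparable. The documents support neither. They give no week-24 P1NP by group, and self-selection on unmeasured factors remains under either method.

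What the objection does not answer is precision, which is given up at any r below 1 under the stated assumptions. Nor does an illustrative list of covariates pre-specify the one that matters most.

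**Conclusion.** The point holds as a cheap improvement, not as an error that invalidates the sub-study. The primary test ignores a measured baseline value. Using it would multiply the variance of the contrast by 0.65 to 0.95 for r between 0.3 and 0.9, assuming equal variances and independent groups. On the form that returns the plan's 44, power would rise from 80% to between 94% and 82%.

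The imbalance point is conditional. The unadjusted contrast shifts by (1−r) times a week-24 difference only if one exists and the groups regress to a common mean. The change score relies on parallel trends, and the adjusted model on no unmeasured confounding given week-24 P1NP. The documents cannot say which assumption is closer to the truth, which is the reason to show both analyses.

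**What to change.** In sub-study section 9.2:

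1. Pre-specify a pair-aware linear model of week-48 log P1NP (or log change) on group and week-24 log P1NP, either as the primary analysis or as a named key sensitivity analysis, and report it beside the paired t-test. A simple version regresses the within-pair difference at week 48 on the within-pair difference at week 24 and reads the effect from the intercept. With 44 pairs this leaves 42 residual degrees of freedom instead of 43.
2. Name week-24 P1NP as a covariate in the regressions already planned.
3. State the analysis scale, so that sections 9.1 and 9.2 agree.
4. Under objective 1.3.4, compare week-24 P1NP and the entry-to-week-24 change between cases and controls, and use this when interpreting any disagreement between the two estimates.

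The cost is wording before analysis; no new samples or assays are needed. The downside is that two estimates may differ, so the text must say in advance which is primary. Neither one removes self-selection.
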